### **3.2.3.2.3 Vertical Jump Efficiency**

This student participant will be evaluate the energy conversion efficiency of lower limb muscles during the jumping-rotating-landing process (e.g., the ratio of squat jump height to ground reaction force), where a power output efficiency exceeding 85% indicates excellent lower limb stiffness and neuromuscular coordination (Markovic & Mikulic, 2010). This metric serves as a training monitoring parameter, and optimization of this efficiency is shown to enhance jumping height. The biomechanical model is expressed as:

$$\text{Efficiency} = \frac{\text{Jump Height}}{\text{Ground Reaction Force} \cdot \cos(\theta)}$$

where the ideal take-off angle  $\theta$  is approximately 30°.

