### **1.3 RESEARCH QUESTIONS**

- (1) What are the differential effects of static, dynamic, and static-dynamic combined balance training on the stability (measured by the maximum distance of single-leg extension and the bilateral symmetry index in the Star Excursion Balance Test (SEBT)) of beginner gymnasts?
- (2) Do static, dynamic, combined balance training induce distinct improvements in jumping mechanics (CMJ/SLCMJ: jump height, PF, RFD, impulse) and kinetic efficiency (jump height/GRF ratio), and does combined training show superior neuromuscular adaptations?
- (3) Among static, dynamic, and static-dynamic combined balance training modalities, which one most effectively minimizes the center of mass (COM) offset distance, body sway amplitude, and landing impact force—while maximizing rotational smoothness and single-leg balance duration—in beginner gymnasts when they perform 360° single-leg standing pirouettes and 360° straight-body jump turns, with all outcomes quantified by 3D motion capture technology?

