Impulse:	In countermovement jumps, impulse is the accumulation of ground reaction force (GRF) over time (the area under the force-time curve) (Claudino et al., 2017). Its net impulse (total impulse minus gravitational impulse) determines the change in human momentum, directly dictating the takeoff velocity and jump height (Painter et al., 2022).
Center of gravity deviation distance	In rotational movements, the center of gravity deviation distance refers to the perpendicular deviation distance of the center of gravity (CoG) relative to the rotation axis—the smaller the deviation, the higher the efficiency of rotational control (Lee et al., 2021).
Joint Angle variation	It refers to the dynamic angular changes in each joint relative to the initial posture, which regulates the moment of inertia and angular momentum by adjusting joint flexion/extension to achieve precise control over rotational speed and stability (Moke et al., 2020).

Vertical Jump Efficiency	It refers to the ability to convert energy generated by muscle contraction (especially the elastic energy stored during the eccentric-concentric contraction cycle and the energy from active force generation) into the gravitational potential energy required for the vertical displacement of the body's center of mass (Kazuaki et al., 2022).
Landing Impact Force	It refers to the instantaneous peak force generated by the ground reaction force (GRF) now the body contacts the ground (Mojaddarasil & Sadigh, 2021a).
Body Oscillation Amplitude	It refers to the maximum displacement of the body's center of mass (or specific segments) relative to the equilibrium position during dynamic movements such as running, jumping, and walking (Pettorossi et al., 2013).
Rotation Smoothness Index	It is a quantitative index used to evaluate the smoothness of the angular velocity time series in rotational movements (such as gymnastic twists and figure skating spins) (Sjölander et al., 2008).

## CHAPTER 2

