## 4.4 Gymnastics skills test results

### 4.4.1 Straight jump 360 ° turn test results

Table 19 Straight jump 360 ° turn test results at baseline and 8 weeks postintervention in the static intervention, dynamic intervention, static-dynamic intervention, and control groups. Data presented as mean  $\pm$  SD.

Group	Test Type	Time Point	Center of gravity deviation distance	Joint Angle variation (°)	Vertical Jump Efficiency (%)	Landing Impact Force (N)	Two-Way Repeated Measures ANOVA	Bonferroni (p)
Static balance group	Straight jump 360 ° turn (Pre-Test)	B						
		W8						
	Straight jump 360 ° turn (Post-Test)	B						
		W8						
Dynamic balance group	Straight jump 360 ° turn (Pre-Test)	B						
		W8						
	Straight jump 360 ° turn (Post-Test)	B						
		W8						
Static and Dynamic balance group	Straight jump 360 ° turn (Pre-Test)	B						
		W8						
	Straight jump 360 ° turn (Post-Test)	B						
		W8						
Control group	Straight jump 360 ° turn (Pre-Test)	B						
		W8						
	Straight jump 360 ° turn (Post-Test)	B						
		W8						

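### Vertical Jump Efficiency, as printed, is a length divided by a force: it is not an energy efficiency or a percentage, cannot be set against 85%, and has no fixed direction of benefit

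*Protocol*

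**What the plan says.** Section 1.6 defines the outcome as converting energy from muscle contraction "into the gravitational potential energy required for the vertical displacement of the body's center of mass". Section 3.2.3.2.3 says it evaluates the "energy conversion efficiency of lower limb muscles during the jumping-rotating-landing process", gives as an example "the ratio of squat jump height to ground reaction force", and prints the model as jump height / (ground reaction force × cos θ), with an ideal take-off angle θ of about 30°. The same section attaches the benchmark "where a power output efficiency exceeding 85% indicates excellent lower limb stiffness and neuromuscular coordination".

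Objective 3 in section 1.4.2 names the measure as one of four outcomes for the straight jump 360° turn. Table 19 (section 4.4.1) gives "Vertical Jump Efficiency" a column in per cent. Research question 2 (section 1.3) uses a related measure for the two countermovement jumps, "kinetic efficiency (jump height/GRF ratio", without the cosine. That ratio appears in neither objective 2 nor Table 17.

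**The concern.** One outcome has three incompatible descriptions: an energy conversion (1.6), a height-to-force ratio (3.2.3.2.3 and, without the angle, 1.3), and a percentage (the 85% benchmark and Table 19). If the formula is followed, the Table 19 column cannot be filled in its stated unit and the benchmark cannot be applied.

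The measure is one of the four straight-jump-turn outcomes behind HA3. Research question 2 relies on a similar ratio when it asks whether combined training gives superior adaptation. A group difference in a quantity with no fixed direction of benefit would not answer either question.

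**Working it through.** **Inputs from the protocol.** Formula, 85% benchmark and θ of about 30°: section 3.2.3.2.3. Jump height in cm and force in N: section 2.5.1. BMI limits 18.5 and 25 kg/m²: section 3.5.1. Vertical jump with the turn: section 3.2.3.2.

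**Inputs assumed, not in the protocol.** Jump height h = 0.20 to 0.30 m; ground reaction force F = 1,100 to 1,400 N. The unit finding in step 1 needs neither.

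**1. Units.** E = h / (F × cos θ). The cosine has no unit, so E is in m/N (or cm/N). An energy efficiency is energy out over energy in and has no unit. The formula contains no work or energy term.

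**2. Trying to reproduce the 85% scale.** cos 30° = 0.866.
- Lowest: 0.20 / (1,400 × 0.866) = 0.20 / 1,212 = 0.00016 m/N.
- Highest: 0.30 / (1,100 × 0.866) = 0.30 / 953 = 0.00031 m/N.
- Multiplied by 100: about 0.016 to 0.031, against 85.
- Height needed for E = 0.85 m/N: 0.85 × 953 = 810 m to 0.85 × 1,212 = 1,030 m.

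Changing units does not rescue the benchmark. The same range is about 16 to 31 in cm/kN, where nobody reaches 85, and about 165 to 315 in mm/kN, where everybody does.

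**3. Body mass.** With equal height and equal force per kg, F is proportional to mass, so E is proportional to 1/mass. At the same stature the mass ratio equals the BMI ratio: 25 / 18.5 = 1.351. The lighter participant scores 35% higher; equivalently, the heavier scores 1 − 18.5/25 = 26% lower. Jump and relative force are identical.

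**4. Direction when force changes.**
- Height fixed, force up: E falls.
- Height +10%, force +15%: 1.10 / 1.15 = 0.957, so E falls 4.3%.
- Constant mean force over a fixed push-off distance s: h = s(F/mg − 1), so h/F = s(1/mg − 1/F), which rises with F. From 2.0 to 2.3 body weights, height goes from 1.0s to 1.3s (+30%) and force rises 15%; 1.30 / 1.15 = 1.130, so E rises 13%.

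All three are possible. The sign depends on whether height or force gains proportionally more.

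**5. Angle.** The reference axis is not given, nor whether θ is measured per trial or held at 30°.
- From vertical: 30° is a tilt. At equal height and force it scores 1 / cos 30° = 1.155 times a vertical take-off, that is, 15.5% more.
- From horizontal: 30° is still further from vertical, and at a vertical take-off cos 90° = 0, so E is undefined.
- Held at 30° for all: the cosine is a constant and does nothing.

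Neither axis makes 30° fit the vertical jump in section 3.2.3.2.

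**The case against.** The strongest reply is that little depends on the label. Table 19 plans a two-way repeated-measures ANOVA on the continuous value. A constant multiplier or a wrong unit leaves F and p unchanged, and no trial decision uses the 85% benchmark. The measure is one of 19 tabulated test outcomes (8 in Table 17, 3 in Table 18, 4 each in Tables 19 and 20). All of that stands. It shows that a test could be computed, not that the result would mean anything.

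Body mass is not a bias between randomised arms, and a stable mass cancels in each participant's proportional change. That also stands: the 35% is a difference between individuals at opposite BMI limits, not an expected difference between arms. Section 3.8.2.1 also mentions body-weight normalisation of the countermovement-jump data, so the mass criticism should not be carried over to the research question 2 ratio. Section 3.2.3.2.3 itself has no such step.

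Three stronger readings are tempting, and the protocol does not support them:
- **The score falls when a gymnast pushes harder.** This holds only at fixed height, or when force gains proportionally more than height.
- **A programme that raises both height and force must show no change or a decline.** Step 4 gives a plausible case in which the score rises.
- **The score falls when she jumps straighter.** This needs θ entered per trial and measured from vertical; the protocol states neither. From horizontal the direction reverses.

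**Conclusion.** The outcome is wrongly defined. The printed formula is a length per force. It does not measure the energy conversion of section 1.6, cannot fill a per cent column, and cannot be judged against 85%. This follows from the units alone. The size, about 0.00016 to 0.00031 m/N, rests on the assumed heights and forces.

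The other defects are that the formula is not mass-normalised, that 30° fits a vertical jump on neither axis, and that the force is unspecified: it could be peak or mean push-off force or, since the section speaks of the whole movement through landing, a landing force. Because height and force can both improve while the score moves either way, a change cannot be read as better or worse. The protocol does not support a claim that the score moves systematically against a successful programme.

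**What to change.** Delete from section 3.2.3.2.3 the formula, the 85% cut-off and the 30° angle, and remove the per cent label from Table 19. For the straight jump turn, report jump height and push-off force per kg as two separate outcomes. State one height method: section 3.2.2.2 uses impulse-momentum and section 3.8.2.1 uses flight time. Drop the height/force ratio from research question 2, since height and peak force are already in Table 17. Bring sections 1.3, 1.4.2 (objective 3), 1.6, 3.2.3.2.3 and 4.4.1 into line.

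Dividing turn height by the participant's own countermovement-jump height would give a true percentage, but I would not substitute it. It puts another training outcome in the denominator and still does not measure energy conversion.

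The cost is wording. The printed formula already requires height and force for this task, so no new test or participant is needed, and Table 22 places recruitment at 1/7/2026, after this version dated 25/9/25. The small downside is lost comparability with any earlier use of the ratio.

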### 3.2.3.2.4 Landing Impact Force (N)

During the landing phase, the peak value of vertical impact force in participants is measured (simulating sudden stop scenarios in competitions), serving as an indicator of lower limb cushioning ability. Injury Prevention Indicator: An impact force below 1,200 N reduces the risk of Achilles tendon injury by 30% (Joseph, 2012), while forces exceeding 1,500 N typically indicate abnormal landing posture (e.g., inward knee buckling leading to stress concentration), providing a basis for technical optimization. The mechanical cushioning model is expressed as:

[figure not shown]
$$F_{\text{buffer}} = \frac{mgh}{t^2}$$

where  $t$  represents cushioning time (ideal value < 0.3 seconds). This model provides a quantitative framework for analyzing the relationship between impact force and motor control efficiency.

### 3.2.3.3 Measurement of Standing Single - leg 360° turn

Participants assume a split stance position with the front leg flexed at 20–30°, weight evenly distributed over the supporting leg, the corresponding arm extended forward, and the contralateral arm naturally positioned at the side. At the start of the test, using the supporting leg as the axis of rotation, participants complete a 360° horizontal rotation around the vertical axis at a constant speed through coordinated control of the hip joint and core muscles. Throughout the movement, fixed head orientation and gaze direction must be maintained to stabilize the rotational axis, while avoiding trunk flexion, extension, or lateral deviation (Fukata et al., 2025). Upon returning to the starting posture after rotation, the trial is deemed valid if

there is no displacement of the supporting foot, the non-supporting leg does not touch the ground, and no loss of balance or sway occurs, the decomposed movements are shown in Figure 9.

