### 3.2.3.2 Measurement of Straight Jump 360° Turn

Participants start in an upright position with feet together and arms raised overhead. During the test, they swing their arms backward, perform a natural squat, and execute an explosive vertical jump upward, synchronizing arm movement to generate momentum. Upon reaching the aerial phase, subjects rapidly engage core muscles to complete a 360° horizontal rotation around the vertical axis, maintaining stable head and gaze direction to control the rotation axis. When landing, contact is made first with the forefoot, transitioning to full-foot support, while maintaining knee flexion  $\leq 30^\circ$ , avoiding lateral hip displacement, and keeping the trunk upright to absorb impact forces (Joseph, 2012). The entire movement must ensure continuity among the takeoff, rotation, and landing phases, with no loss of balance or deviation in the rotation axis, the decomposed movements are shown in Figure 8.

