#### 3.2.3.2.1 Center of Gravity Deviation

The athlete executes a two-leg takeoff and completes a 360° aerial rotation around the hip joint as the axis, requiring the maintenance of body balance upon landing. During the test, this metric is defined as the maximum distance by which the three-dimensional displacement of the center of gravity (COG) deviates from the ideal rotational path (Hechenblaikner, 2024). Dynamic Balance Control: Smaller values indicate stronger ability of the central nervous system to

regulate aerial posture and higher landing stability. Biological Explanation: The mechanical model is expressed as

$$D = \sqrt{(X \text{ real} - X \text{ ideal})^2 + (y \text{ real} - y \text{ ideal})^2 + (Z \text{ real} - Z \text{ ideal})^2}$$

where X, Y, Z represent the actual COG coordinates versus the ideal trajectory coordinates (Etkin & Reid, 1995).

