### 3.2.3.3.1 Center of Gravity Deviation

The student participant completes a 360° rotation around the axis of one leg, with the other leg off the ground, and maintains static balance. During the test, the student participant must keep the torso stable during high-speed rotation to avoid imbalance caused by the deviation of the center of gravity. To assess performance, the three-dimensional displacement of the center of mass is tracked via an Inertial Measurement Unit (IMU), and the overlap degree between the actual trajectory and the ideal path is calculated using the formula

$D = \sqrt{(X \text{ real} - X \text{ ideal})^2 + (y \text{ real} - y \text{ ideal})^2 + (Z \text{ real} - Z \text{ ideal})^2}$  ; smaller values indicate higher neuromuscular coordination and stronger action stability (Farana et al., 2023).

The Vicon high-speed camera system (200 Hz) captures the movement trajectory, and center of mass deviation is calculated in combination with an inverse dynamics model, while ground reaction force is measured by a Force Plate (sampling rate 1 kHz) to provide biomechanical validation of balance control (Karatsidis et al., 2019).

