### **3.2.3.3.2 Body Oscillation Amplitude (m)**

During the dynamic single-leg support rotation, student participants are required to maintain the other leg completely off the ground while keeping the spine in a stable neutral position, with measurements taken for the maximum lateral/longitudinal displacement of the torso and lower limbs (e.g., lateral sway of the upper body during rotation). This assessment evaluates core stability by reflecting the anti-interference capability of deep core muscle groups (e.g., transversus abdominis, multifidus) against rotational centrifugal force (Vasseljen et al., 2012). The oscillation amplitude serves as an action economy indicator, with a positive correlation to energy consumption—optimizing this parameter can enhance movement efficiency, as described by the theoretical model  $E_{loss}=k \cdot A^2$  (where A represents oscillation amplitude). Using high-speed photography ( $\geq 200$  Hz), movement trajectories are captured and combined with a rigid body dynamics model to calculate three-dimensional oscillation amplitudes. Insufficient activation of core muscles, as noted by Gribble et al., 2012, often leads to compensatory excessive abduction/adduction of the hip joint, highlighting the neuromuscular mechanisms underlying rotational stability.

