### **3.8.2 Research tool**

#### **3.8.2.1 Kunwei Force Plate (jumping test)**

The Kunwei force plate is a high-precision biomechanical measurement device widely used to assess jump performance, balance, and force development in athletes (Cormie et al., 2007). To scientifically evaluate the biomechanical performance of the countermovement jump (CMJ) and single-leg countermovement jump (SLCMJ), the standardized testing protocol using the

Kunwei Force Plate is as follows: Participants stand barefoot on the force plate with arms relaxed to complete a 10-second static calibration, recording baseline center of pressure (CoP) trajectories (re-test required if CoP drift exceeds 2 cm), with the system sampling rate set to 1000 Hz. For CMJ testing, participants perform rapid countermovement jumps from self-selected knee flexion depth to maximal height, landing symmetrically and stabilizing for 2 seconds, repeated 5 times (60-second rest intervals) (Markovic et al., 2004). For SLCMJ, participants execute single-leg jumps followed by ipsilateral landing with 3-second balance maintenance; failed trials (contralateral limb contact or external support) trigger retesting. The force plate continuously acquires vertical ground reaction force (vGRF) to calculate jump height (flight time method:  $h = \frac{g \times t^2}{8}$  ) peak force (max vGRF), rate of force development (RFD: slope of force-time curve from 0-200 ms), and impulse (force-time integral). Real-time feedback on adjacent screens highlights critical metrics (e.g., RFD < 3000 N/s—optimize ankle stiffness or bilateral peak force asymmetry > 10%—adjust symmetry). Raw data undergo Butterworth low-pass filtering (50 Hz cutoff) and body weight normalization, with outliers excluded based on predefined criteria (e.g., pre-activation force exceeding 5% body weight or stabilization time > 1.5 seconds). Processed datasets are encrypted and stored as CMJ/SLCMJ-Date-Subject. This protocol quantifies lower-limb explosive power, bilateral symmetry, and energy transfer efficiency (Gathercole et al., 2015), supporting athlete selection, training monitoring, and rehabilitation assessment (Meylan & Malatesta, 2009).

Figure 11 Kunwei Force Plate

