### 3.8.2.3 TecnoBody 3D Motion Capture System (gymnastic performance movements)

To accurately assess the biomechanical parameters of the 360° straight jump turn and single-leg standing rotation, experimental procedures must integrate standardized protocols with real-time interaction: Test operators first instruct participants to stand still while reflective markers are affixed to anatomical landmarks (acromion, anterior superior iliac spine, greater trochanter, and lower limb joints), emphasizing that "markers must align with bone structures—avoid movement to prevent displacement (Soylu et al., 2025). During static calibration, participants are directed to stand naturally at the center of the force platform with arms relaxed and gaze forward, maintaining stillness for 10 seconds to establish the skeletal model. For formal testing, the straight jump turn requires execution under the command jump vertically, complete a 360° mid-air rotation, and land stably, while the single-leg rotation emphasizes upright posture on the support leg, stable trunk alignment, and 2-second balance maintenance post-rotation, with each movement repeated three times to ensure data reliability. During acquisition, the system provides real-time alerts such as "right knee marker

occluded—adjust arm posture and retest" or "insufficient rotational angular velocity—reduce trunk compensation," ensuring movement standardization. Coaches view screens displaying the participant's center of mass trajectory (red) overlaid with the ideal biomechanical model (green), accompanied by feedback like "0.2-second delay in hip extension—optimize takeoff sequencing." Post-test, data undergoes quality control screening (e.g., center-of-mass deviation standard deviation  $<1.5$  cm, marker occlusion rate  $<5\%$ ), encrypted and stored under the naming convention 'action-date' for subsequent biomechanical modeling and training optimization. This protocol, combining movement standardization, real-time correction, and multimodal data integration, enables granular analysis of rotational techniques (Bravi et al., 2023), supporting technical refinement and injury prevention research in disciplines such as artistic gymnastics and dance.

Figure 13(a) The 3D Motion Capture System

[figure not shown]

Figure 13(b) The Schematic placements of the motion capture system

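### Single-leg turn trials count only if there is no sway or loss of balance, and turn recordings are screened on centre-of-mass deviation, so trials are selected on, or close to, the outcomes and effects on them shrink

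*Protocol*

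**What the plan says.** **Validity rule, single-leg turn (Protocol 3.2.3.3).** After the return to the starting posture, the trial counts only when the foot that bears the weight has stayed in place and "the non-supporting leg does not touch the ground, and no loss of balance or sway occurs". No numeric threshold is given for sway or for loss of balance.

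**Data screen, both turns (Protocol 3.8.2.3).** Each movement is repeated three times. After the test, "data undergoes quality control screening (e.g., center-of-mass deviation standard deviation" below 1.5 cm, listed together with a marker-occlusion rate below 5%).

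**Outcomes of the same movements.**
- Single-leg turn, body oscillation amplitude (3.2.3.3.2): the "maximum lateral/longitudinal displacement of the torso and lower limbs (e.g., lateral sway of the upper body during rotation").
- Single-leg turn, centre-of-gravity deviation (3.2.3.3.1), of which "smaller values indicate higher neuromuscular coordination and stronger action stability".
- Jump turn, centre-of-gravity deviation (3.2.3.2.1): the "maximum distance by which the three-dimensional displacement of the center of gravity (COG) deviates from the ideal rotational path".

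Specific objective 3 names these measures, and they are columns of Tables 19 and 20.

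**Jump turn instruction (Protocol 3.2.3.2).** The movement is to be performed "with no loss of balance or deviation in the rotation axis". No clause here says that a trial is invalid, discarded or repeated.

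The protocol does not provide for logging failed turn attempts. It also does not say what happens to a participant who has no valid turn trial.

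**The concern.** A rule on which trials count should pick out technical faults, such as an occluded marker or a movement that was not the one being tested. Here the rule for the single-leg turn refers to sway, and sway in that movement is an outcome. The data screen places a centre-of-mass criterion next to marker occlusion, as though a large deviation were a recording fault and not a poor performance.

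The participants are beginners with at most one year of systematic training, so failed turns are plausible, above all at baseline. A common cut-off removes more trials where stability is worse. If training works, that is at baseline and in the arms that improve least. The remaining trials look more alike than the participants are, and both the pre-post change and the differences between arms are understated. Because failed attempts are not logged, the loss could be neither measured nor corrected later.

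**Working it through.** **Step 1. Criteria against outcomes.**

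| Criterion | Where | Related outcome | Status |
|---|---|---|---|
| No sway, no loss of balance | 3.2.3.3 | Body oscillation amplitude and centre-of-gravity deviation, single-leg turn | Explicit validity rule |
| SD of centre-of-mass deviation < 1.5 cm | 3.8.2.3 | Centre-of-gravity deviation, both turns | Screen, given as an example; SD within or across trials not stated |
| No axis deviation, no loss of balance | 3.2.3.2 | Centre-of-gravity deviation, jump turn | Performance instruction only |

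Tables 19 and 20 list eight outcomes, four per movement. Three of them meet a criterion of this kind directly: centre-of-gravity deviation in both tables and oscillation amplitude in Table 20.

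**Step 2. Size under stated assumptions.** The protocol gives no failure rate, no outcome SD and no expected effect on these measures, so there is no figure of its own to reproduce. The following inputs are assumptions: normal trial scores with lower values better; control N(0, 1); treated N(−0.5, 1); one cut-off c for everyone; a trial is kept if its score is below c.

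With a = c − μ and λ = φ(a)/Φ(a), the kept trials have mean μ − λ and variance 1 − aλ − λ². The rejected share is 1 − Φ(a).

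Worked case with 20% of control trials rejected, c = 0.8416:
- Control: λ = 0.2800/0.8000 = 0.350; mean −0.350; variance 0.583.
- Treated: a = 1.3416; λ = 0.1622/0.9101 = 0.178; mean −0.678; variance 0.729; rejected 9.0%.
- Mean difference: 0.678 − 0.350 = 0.328.
- Observed SD: √[(0.583 + 0.729)/2] = 0.810. Standardised difference: 0.328/0.810 = 0.41.

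| Control trials rejected | Treated trials rejected | Mean difference (original SD; true 0.50) | Difference in observed-SD units |
|---|---|---|---|
| 10% | 3.7% | 0.39 | 0.44 |
| 20% | 9.0% | 0.33 | 0.41 |
| 50% | 30.9% | 0.21 | 0.32 |

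The last column falls less because truncation also narrows the spread.

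**Step 3. Check with repeated attempts.** A simulation let each participant try until three trials were valid (at most 40 attempts), with a true difference of 0.70 trial-level SD and a between-trial intraclass correlation (ICC) of 0.5 to 0.9.

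| Untrained trials that pass | Share of the mean difference kept | Standardised difference at ICC 0.7 (true 0.78) |
|---|---|---|
| 90% | 0.86–0.88 | 0.77 |
| 70% | 0.66–0.67 | 0.70 |
| 50% | 0.48–0.49 | 0.62 |
| 30% | 0.31–0.33 | 0.51 |

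At ICC 0.7 and a 50% pass rate, 84% of untrained and 96% of trained participants reached three valid trials, so the selection also acts on who is analysed. The effect shrank in every scenario.

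**The case against.** The best defence is that the rule in 3.2.3.3 may apply only at the finish. It is introduced at the return to the starting posture, and 3.8.2.3 asks for a 2-second balance hold after the rotation, whereas the oscillation outcome is measured during the rotation. The criterion and the outcome would then be different quantities. This reading is possible, but it does not remove the problem: balance at the finish is likely to go with sway during the turn, so trials would still be selected close to the outcome.

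The screen in 3.8.2.3 is also open to a milder reading. It is an example, the SD is undefined, and the consequence of failing it is not stated. An SD across repetitions would be a check of repeatability. The text does not settle this, so the screen supports the point less firmly than the validity rule does.

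Four stronger readings are tempting, and the protocol does not support them:
- A reader might infer that jump turns with axis deviation are rejected. Section 3.2.3.2 only tells participants how to perform the movement.
- A reader might count the force-plate exclusion in 3.8.2.1 ("pre-activation force exceeding 5% body weight or stabilization time > 1.5 seconds") as the same fault. It concerns the countermovement jumps, whose outcomes in Table 17 are jump height, peak force, rate of force development and impulse. Stabilisation time is not among them.
- A reader might extend the bias to every turn outcome. Rotation smoothness, landing impact force, joint angle variation and vertical jump efficiency are not truncated directly.
- A reader might conclude that all performance-based rejection should go. A turn with a touch-down or a displaced supporting foot is not the movement that 3.2.3.3 defines, and excluding it is ordinary practice.

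**Conclusion.** The concern stands for the sway and loss-of-balance conditions in 3.2.3.3 and, less firmly, for the centre-of-mass SD criterion in 3.8.2.3. Read literally, a trial without sway leaves the sway outcome almost nothing to measure. Read loosely, the assessor decides how much sway is too much. In both cases poor performances are removed on, or close to, an outcome.

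The direction, toward no effect, follows if training improves stability and the same cut-off is applied in all arms and at both visits. The size is not known. Under the assumptions in the working, a true 0.5 SD becomes 0.39 to 0.21 original SD, or 0.44 to 0.32 in observed-SD units. A sharp cut-off placed exactly on the outcome is the unfavourable case; a criterion only correlated with the outcome would attenuate less.

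The stability test and jump outcomes of objectives 1 and 2 are not affected by these turn rules.

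**What to change.** 1. In 3.2.3.3, delete the sway condition from the validity rule, and delete loss of balance wherever it goes beyond touch-down or displacement of the supporting foot.
2. Keep the touch-down and foot-displacement conditions as the definition of a completed turn.
3. In 3.8.2.3, remove the centre-of-mass deviation SD from the quality screen. Keep technical criteria such as marker occlusion.
4. In 3.2.3.2, state that the wording on balance and rotation axis is an instruction to the participant and not a ground for rejecting a trial.
5. Log every failed attempt with its reason, by arm and visit, so that differential rejection can be reported.

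The cost is a change to test-procedure and data-cleaning wording plus a short attempt log. The drawback is somewhat noisier trial data. The change needs to be in place before data collection, which Table 22 dates to 1/9/2026, because trials that are discarded and not logged cannot be recovered.
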